6.2.2.2. Sensitivity analyses for progression-free survival

The following sensitivity analyses will be performed to explore the robustness of the primary analysis results. These analyses are regarded as purely exploratory. The sensitivity analyses will repeat the primary analysis (p-value, HR and 95% CIs) described in Section 6.1.2.1 with the modifications below:

- PFS based on BICR assessment and counting all PD and deaths as events regardless of missing assessments or timing of the event
- PFS based on BICR assessment on the PP analysis set for PFS
- PFS based on BICR assessment using an unstratified analysis
- PFS based on BICR assessment using strata derived according to eCRF data instead of those entered in IRT. See Section 6.2.2.1 for the derivation associated with the stratification factor of bulky disease.
- PFS based on BICR assessment modifying the censoring rules in Table 9 to consider all deaths as events
- PFS based on BICR assessment modifying the censoring rules in Table 9 with initiation of subsequent anti-cancer therapies not used as a censoring reason

Methods for evaluating the validity of model assumptions

The same methodology described in Section 6.2.2.1 for OS will be used for PFS based on BICR assessment.

BICR vs Investigator assessment

A summary of the BICR assessment versus investigator assessment will be provided including numbers of concordant and discordant assessments as well as the number of cases where PFS event was assessed at different timepoints based on BICR and investigator assessments.

Table 11 outlines the possible outcomes by investigator and BICR (Amit et al. 2011).

Table 11. Possible Outcomes for Investigator vs BICR

		BICR	
		Event	No Event
Investigator	Event	$a = a_1 + a_2 + a_3$	b
	No Event	c	d

a1: number of agreements on timing and occurrence of event;
 a2: number of times agreement on event but INV declares event later than BICR;
 a3: number of times agreement on event but INV declares event earlier than BICR;
 $N = a + b + c + d$.

The timing agreement of event is defined as a window of ± 7 days.

The following measure of discordance will be calculated for each treatment arm:

- Total Event Discrepancy Rate: $(b+c) / N$
- Early Discrepancy Rate (EDR): $(a_3+b) / (a+b)$
- Late Discrepancy Rate (LDR): $(a_2+c) / (a_2+a_3+b+c)$
- Overall Discrepancy Rate: $(a_2+a_3+b+c) / N$

The EDR represents the positive predictive value of investigator assessment and quantifies the frequency with which the investigator declares PFS event earlier than BICR within each treatment arm as a proportion of the total number of investigator assessed events.

The LDR quantifies the frequency with which the investigator declares PFS event later than BICR as a proportion of the total number of discrepancies within the treatment arm.

Discordance metrics are calculated for each treatment arm and, for each metric, the difference in discordance between the experimental and control arms is used to evaluate potential bias. If the discordance is similar across the treatment arms then this suggests the absence of evaluation bias favoring a particular treatment arm. A negative differential discordance for EDR and/or a positive differential discordance for LDR may be indicative of investigator evaluation bias in favor of the experimental arm (Amit et al, 2011).

Exploratory analyses to investigate the impact of potential prognostic or effect modifying (predictive) factors

The same methodology described in Section 6.2.2.1 for OS will be used for PFS based on BICR assessment.

090177e19142bcd4\Approved\Approved On: 09-Jul-2019 05:44 (GMT)

6.2.2.3. Objective response and tumor shrinkage

Best overall response (BOR) will be assessed based on reported overall lesion responses at different evaluation time points from the date of randomization until the first documentation of PD, according to the following rules.

BOR Based on Confirmed Responses:

- CR = at least two determinations of CR at least 4 weeks apart and before first documentation of PD
- PR = at least two determinations of PR or better (PR followed by PR or PR followed by CR) at least 4 weeks apart and before first documentation of PD (and not qualifying for a CR)
- SD (applicable only to patients with measurable disease at baseline) = at least one SD assessment (or better) ≥ 6 weeks after the date of randomization and before first documentation of PD (and not qualifying for CR or PR).
- Non-CR/non-PD (applicable only to patients with non-measurable disease at baseline) = at least one non-CR/non-PD assessment (or better) ≥ 6 weeks after the date of randomization and before first documentation of PD (and not qualifying for CR or PR).
- PD = first documentation of PD ≤ 12 weeks after the date of randomization (and not qualifying for CR, PR, SD or non-CR/non-PD).
- NE: all other cases.

Only tumor assessments performed on or before the start of any further anti-cancer therapies will be considered in the assessment of BOR. Clinical deterioration will not be considered as documented disease progression.

An objective status of PR or SD cannot follow one of CR. SD can follow PR only in the rare case that tumor increases by less than 20% from the nadir, but enough that a previously documented 30% decrease from baseline no longer holds. If this occurs, the sequence PR-SD-PR is considered a confirmed PR. A sequence of PR – SD – SD – PD would be a best response of SD if the window for SD definition has been met.

Objective Response (OR) is defined as a confirmed BOR of CR or PR according to RECIST v1.1. Both CR and PR must be confirmed by repeat assessments performed no less than 4 weeks after the criteria for response are first met.

Patients who do not have a post-baseline radiographic tumor assessment due to early progression, who receive anti-tumor therapies other than the study treatments prior to reaching a CR or PR, or who die, progress, or drop out for any reason prior to reaching a CR or PR will be counted as non-responders in the assessment of OR. Each patient will have an objective response status (0: no OR; 1: OR). OR rate (ORR) is the proportion of patients with OR in the analysis set.

ORR by treatment arm will be calculated along with the 2-sided 95% CI using the Clopper-Pearson method (exact CI for a binomial proportion as computed by default by the FREQ procedure using the EXACT option).

In addition, the frequency (number and percentage) of patients with a confirmed BOR of CR, PR, SD, non-CR/non-PD (applicable only to patients with non-measurable disease at baseline), PD and NE will be tabulated. Patients with confirmed BOR of NE will be summarized by reason for having NE status. The following reasons will be used:

- No baseline assessment
- No post-baseline assessments due to death
- No post-baseline assessments due to other reasons
- All post-baseline assessments have overall response NE
- New anti-cancer therapy started before first post-baseline assessment
- SD of insufficient duration (<6 weeks after the date of randomization without further evaluable tumor assessments)
- PD too late (>12 weeks after the date of randomization)

Special and rare cases where BOR is NE due to both SD of insufficient duration and late PD will be classified as ‘SD of insufficient duration’.

The association of study treatment and OR will be tested by the General Association Statistic of the [Cochran-Mantel-Haenszel test \(CMH\)](#) with the randomization strata taken into account. The null hypothesis of no association in any of the randomization strata is tested against the alternative, which specifies that there is an association between study treatment and tumor response at least in one randomization stratum. The CMH test will be performed at 1-sided alpha level of 0.025.

The stratified odds ratio in terms of OR will also be estimated along with its 95% CI to compare study treatments. The odds ratio is defined as the odds of OR with experimental treatment divided by the odds of OR with control treatment. The Breslow-Day test will be used to check the homogeneity of the odds ratio across the randomization strata. It tests the null hypothesis that odds ratios in all strata are equal against the alternative hypothesis that at least in one stratum the odds ratio is different.

In case the null hypothesis of homogeneity of odds ratios across strata is not rejected at the 2-sided alpha level of 0.05, the common odds ratio will be determined using the Mantel-Haenszel estimate (by the FREQ procedure using CMH option in SAS); if the null hypothesis of homogeneity of odds ratio across all strata is rejected, the odds ratio per stratum will be calculated with the corresponding exact CI.

BICR vs Investigator Assessment:

Table 12 outlines the possible BOR outcomes by investigator and BICR.

Table 12. Possible BOR Outcomes for Investigator vs BICR

BOR		BICR Assessment					
		CR	PR	SD	Non-CR/ non-PD	PD	NE
Investigator Assessment	CR	n ₁₁	n ₁₂	n ₁₃	n ₁₄	n ₁₅	n ₁₆
	PR	n ₂₁	n ₂₂	n ₂₃	n ₂₄	n ₂₅	n ₂₆
	SD	n ₃₁	n ₃₂	n ₃₃	n ₃₄	n ₃₅	n ₃₆
	Non-CR/ non-PD	n ₄₁	n ₄₂	n ₄₃	n ₄₄	n ₄₅	n ₄₆
	PD	n ₅₁	n ₅₂	n ₅₃	n ₅₄	n ₅₅	n ₅₆
	NE	n ₆₁	n ₆₂	n ₆₃	n ₆₄	n ₆₅	n ₆₆

$\sum_{i=1}^6(n_{ii})$ is the number of agreements on BOR between BICR and Investigator

$\sum_{i,j=1}^6(n_{ij})$ for $i \neq j$ is the number of disagreements on BOR between BICR and Investigator

$N = \sum_{i,j=1}^6(n_{ij})$

The following measures of concordance will be calculated for each treatment arm:

- Concordance rate for BOR = $\sum_{i=1}^6(n_{ii}) / N$
- Concordance rate for response = $[\sum_{i,j=1}^2(n_{ij}) + \sum_{i,j=3}^6(n_{ij})] / N$

Concordance rates are calculated for each treatment arm and, for each metric, the difference in concordance between the experimental and control arms are used to evaluate potential bias. If the concordance is similar across the treatment arms then this suggests the absence of evaluation bias favoring a particular treatment arm.

Tumor Shrinkage from baseline:

Tumor shrinkage will be summarized as the percent change from baseline in target lesions (sum of longest diameter for non-nodal lesion and short axis for nodal lesion) per time point. It will be derived as:

- $((\text{Sum of target lesions at week XX} - \text{sum of target lesions at baseline}) / \text{sum of target lesions at baseline}) \times 100$

090177e19142bcd4\Approved\Approved On: 09-Jul-2019 05:44 (GMT)

The maximum reduction in target lesions from baseline will be derived across all the post-baseline assessments until documented disease progression, excluding assessments after start of subsequent anti-cancer therapy, as:

- Minimum of $((\text{sum of target lesions at week XX} - \text{sum of target lesions at baseline}) / \text{sum of target lesions at baseline}) \times 100$

A waterfall plot of maximum percent reduction in the sum of longest diameter for non-nodal lesions and short axis for nodal lesions from baseline will be created by treatment arm. These plots will display the best percentage change from baseline in the sum of the diameter of all target lesions for each patient with measurable disease at baseline and at least one post-baseline assessment.

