European Union (EU) and US in combination with paclitaxel, pegylated liposomal doxorubicin (PLD), or topotecan, for the treatment of patients with platinum-resistant recurrent ovarian cancer. This approval was based on results of the AURELIA study, which randomized patients to physician's choice of chemotherapy (PLD, paclitaxel, or topotecan) with or without bevacizumab, and included patients with more than one prior line of platinum based chemotherapy. This study demonstrated improvement in median progression-free survival (PFS) from 3.4 months to 6.7 months (HR=0.48, 95 % CI: 0.38 to 0.60, p<0.001). No statistically significant improvement in OS was seen.⁵ In 2014, olaparib, a (Poly ADP ribose polymerase) PARP inhibitor, was approved for the treatment of patients with advanced Breast Cancer Antigen (BRCA)-mutated ovarian cancer by European Medicines Agency (EMA and Federal Drug Administration (FDA)).⁶

Single-agent PLD has been extensively studied in platinum-resistant ovarian cancer, with response rates of 10-20%, median PFS times of 2.1-3.7 months, and median OS ranging from 8.4 to 16.8 months.^{20,21,22,23,24,25} The approved dose of PLD in the US and EU is 50 mg/m² intravenously every 4 weeks; however, 40 mg/m² every 4 weeks is commonly used in clinical practice and in clinical trials including the AURELIA study.²⁵

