2.2. Study Design

This is a Phase 3, multicenter, randomized, open-label, parallel 3-arm study in which approximately 550 patients will be randomized in a 1:1:1 ratio to receive avelumab alone, avelumab in combination with PLD, or PLD alone, as follows:

- Arm A: avelumab alone;
- Arm B: avelumab plus PLD;
- Arm C: PLD alone.

Patients will be stratified by platinum-refractory or platinum-resistant status, number of prior regimens (1 vs 2 or 3), and bulky disease (defined as presence of a tumor ≥ 5 cm) vs not. Cross-over will not be permitted.

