3.4.2. Baseline characteristics

Randomization is stratified by the following, as recorded in the Interactive Response Technology (IRT):

090177e19142bcd4\Approved\Approved On: 09-Jul-2019 05:44 (GMT)

- Platinum-refractory or platinum-resistant status
- Number of prior regimens (1 vs 2 or 3)
- Bulky disease (defined as presence of a tumor ≥ 5 cm) vs not

The primary analyses of OS and PFS will be stratified by these randomization stratification factors.

Other baseline characteristics (including demographics, physical measurements, disease history and prior anti-cancer therapies) are described in Section 6.5.1. These baseline characteristics are not planned to be included as stratification variables or covariates in statistical models unless otherwise specified in Section 6.

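### The objective-response test pairs a non-directional CMH chi-square with a one-sided level of 0.025, and the SAP gives no rule for direction

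*SAP*

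**What the plan says.** SAP 6.2.2.3 makes three consecutive statements about OR.

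- The association with treatment is "tested by the General Association Statistic of the" CMH test, taking the randomization strata into account.
- The null of no association in any stratum is set against an alternative "which specifies that there is an association between study treatment and tumor response at least in one randomization stratum".
- Its next sentence fixes the significance level: "The CMH test will be performed at 1-sided alpha level of 0.025".

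The section then plans a stratified odds ratio with a 95% CI: "The odds ratio is defined as the odds of OR with experimental treatment divided by the odds of OR with control treatment". It also plans a Breslow-Day test of homogeneity at a two-sided level of 0.05. It does not mention a signed statistic, a check of sign or a conversion of the p-value.

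Protocol 9.3.2 plans response rates by arm with exact two-sided 95% CIs and no test of OR. The SAP sentence is therefore the only specification of this test.

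**The concern.** The General Association statistic measures distance from the null and not its sign, and the stated alternative has no direction either. A one-sided level needs a direction. Two programmers could follow this text faithfully, apply different rejection rules and reach opposite conclusions from the same data.

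The SAP is explicit about sidedness elsewhere. OS and PFS have directional alternatives (HR below 1, SAP 5.1.1), signed z boundaries (Table 5) and one-sided log-rank tests (6.1.1.1 and 6.1.2.1). The subgroup log-rank tests are labelled two-sided (6.4).

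What is at stake is the level and direction of the only formal test of tumour response, and its agreement with the odds-ratio interval reported beside it.

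**Working it through.** **Inputs**

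- Sample size: "approximately 550 patients will be randomized in a 1:1:1 ratio" (SAP 2.2), so 550/3 is about 183 per arm.
- Strata: three binary factors (SAP 3.4.2), including "Number of prior regimens (1 vs 2 or 3"), giving 2 × 2 × 2 = 8 cells. Equal cell sizes are an assumption of the simulation.
- Control response rate: Protocol 1.2.1 gives single-agent PLD "response rates of 10-20" percent. The experimental rates used for power are assumptions.
- Stated level: one-sided 0.025.

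**Step 1: the statistic.** For one experimental arm against control in K strata, Q = Z², where Z = Σ(x − E)/√ΣV. In each stratum x is the number of experimental responders, and E and V are its hypergeometric mean and variance. Q has 1 degree of freedom. The definition of the odds ratio points to pairwise comparisons. A joint test of three arms would have 2 degrees of freedom and no one-sided form.

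**Step 2: three ways to apply 0.025**

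| Reading | Rejects when | Total size | Favouring experimental | Favouring control |
|---|---|---|---|---|
| (a) signed root | Z > 1.960 | 0.025 | 0.025 | 0 |
| (b) chi-square p < 0.025 | Q > 5.024 (Z beyond ±2.241) | 0.025 | 0.0125 | 0.0125 |
| (c) halved p < 0.025, sign not checked | Q > 3.841 (Z beyond ±1.960) | 0.05 | 0.025 | 0.025 |

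A simulation (200,000 runs, 183 per arm, 8 equal strata, common response rate 10%, 15% or 20%) agrees. Reading (a) gives 0.0243 to 0.0253. Reading (b) gives 0.0244 to 0.0252 in total, with 0.0120 to 0.0126 favouring experimental. Reading (c) gives 0.0492 to 0.0501 in total, with 0.0246 to 0.0249 favouring control. The SAP's stated level is reproduced for superiority alone only under (a), which needs a rule the SAP does not contain.

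**Step 3: power under (a) and (b).** Power = Φ[(Δ − z·s0)/s1], with s0 = √(2p̄(1 − p̄)/183) and s1 = √((p1(1 − p1) + p2(1 − p2))/183).

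- 10% versus 20%: s0 = 0.03733, s1 = 0.03696.
  - (a): (0.1 − 1.960 × 0.03733)/0.03696 = 0.726, power 76.6%.
  - (b): (0.1 − 2.241 × 0.03733)/0.03696 = 0.442, power 67.1%.
- 15% versus 25%: s0 = 0.04182, s1 = 0.04149.
  - (a): 0.435, power 66.8%.
  - (b): 0.151, power 56.0%.

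The stratified simulation gives 77.4% and 68.0% for the first pair, and 67.2% and 56.3% for the second.

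**Step 4: when control is better.** With true rates of 10% on control and 5% on experimental (assumed), the simulation flags a difference favouring control in 33% of trials under (b) and 44% under (c). Under (a), significance is declared in 0.01% of trials.

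**Step 5: agreement with the interval.** If the chi-square p-value lies between 0.025 and 0.05 (Z between 1.960 and 2.241), reading (b) calls the result not significant, while the 95% CI for the odds ratio will generally exclude 1.

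**Step 6: place in the error control.** SAP 5.1.1 allocates 2 × 0.0115 + 2 × 0.001 = 0.025 to OS and PFS, with a further procedure for time to deterioration. OR is not in this family.

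**The case against.** The best defence is that the intended meaning can be recovered. The odds ratio is defined as experimental over control, the primary hypotheses are one-sided superiority, and one-sided 0.025 is the usual companion of two-sided 0.05. On that view the sentence means reading (a), and an odds ratio below 1 would stop anyone from presenting a control-favouring result as benefit. Reading (b) is also conservative: its total size is 0.025, with no inflation.

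Much of this stands. Reading (a) is probably what was meant, and the reported estimates would show the direction. But the sentence just before the level states an alternative without direction, so the inference goes against the text, and a SAP should not leave a rejection rule to inference.

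Two stronger readings are tempting, and neither is supported.

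- A reader might infer that no one-sided version of this test exists. In a pairwise comparison one follows directly from the signed root.
- A reader might infer that CMH is invalid for the stated hypotheses. It is valid under the stated null, and the alternative is the logical complement of that null. Opposite effects across strata cost power and do not distort the level. The SAP also plans a Breslow-Day test and, if homogeneity is rejected, odds ratios by stratum.

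**Conclusion.** Wrong as written, with a small consequence. A non-directional statistic and alternative are tied to a one-sided level with no rule to connect them. Read literally, the level for superiority is 0.0125, or 0.025 of a total size of 0.05 falls in favour of control. Halving applies to the superiority direction only.

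The loss of about 10 percentage points of power (about 77% to 67%, or 67% to 56%) is an illustration. It rests on assumed response rates and about 183 per arm. The documents give no design response rate and no power target for OR.

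A reader might take OR to be the leading secondary endpoint, or think that this affects the trial's main claims. The documents support neither. Protocol 2.2 lists objective response, duration of response and disease control together without ranking, and SAP 3.2.2 lists investigator-assessed PFS first. OR is outside the alpha-controlled family, and no interim stopping rule uses it. The correction is desirable, and no primary conclusion depends on it.

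**What to change.** Replace the sentence on the level in SAP 6.2.2.3 with one of the following:

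1. The CMH p-value is compared with two-sided 0.05.
2. The signed root of the CMH statistic is tested at one-sided 0.025 for a common odds ratio (experimental over control) above 1.

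Reword the alternative to match: a common odds ratio different from 1 under option 1, or above 1 under option 2. State that each experimental arm is compared separately with control. Either option brings the test into line with the 95% CI already planned.

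The cost is a sentence or two in the SAP, with no new data and no additional analysis.

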1.2.2.4. Efficacy and Safety in Patients with Ovarian Cancer

Single-agent avelumab activity at 10 mg/kg Q2W was evaluated in heavily pretreated epithelial ovarian cancer (EOC) patients in an ovarian-specific expansion cohort in Study EMR100070-001. Patients with ovarian cancer whose disease progressed on standard therapy were eligible. 75 patients were enrolled from Nov 2013 to Nov 2014. Median age was 62 years (range 38-84 years); ECOG performance status was 0 (41%) or 1 (59%); median number of prior therapies for locally advanced or metastatic disease (excluding adjuvant treatment) was 4 (range, 0-10). At the data cutoff of February 13, 2015, median duration of treatment with avelumab was 12 weeks (range 2-54 weeks), and 8 patients remained on treatment. Eight patients (10.7%, 95% CI, 4.7%, 19.9%) achieved an unconfirmed best objective response (BOR) of partial response (PR). Five out of 8 responses were ongoing at the time of data cutoff. Thirty-three (44%) patients had stable disease. Two additional patients had partial response by immune-related response criteria. Median progression-free survival was 11.4 weeks.

Avelumab was well-tolerated in the ovarian cancer expansion cohort (n=75). Table 3 demonstrates treatment-related adverse events observed in $\geq 5\%$ of patients. The following Grade 3 avelumab-related adverse events were observed in a total of 6 patients (8.0%): one event each of peripheral edema, localized edema, increased lipase, increased blood creatine phosphokinase, arthritis, myositis, hyperglycemia, anemia, tumor pain. There were no Grade 4 or 5 AEs related to avelumab reported in this cohort. Related serious TEAEs were observed in 3 patients (4.0%): Dyspnea (1), pyrexia (1), non-cardiac chest pain (1), flushing (1), localized edema (1), and peripheral edema (1). Immune-related TEAEs were seen in 8 patients (10.7%) and included hypothyroidism (5; 6.7%), arthritis (2; 2.7%), and myositis (1; 1.3%). No drug-related intestinal obstruction or perforations occurred. Discontinuation related to treatment with avelumab was reported in 9 patients (12.0%) [Pfizer/Merck KGaA data on file, cutoff 13 February 2015].⁴⁵

Table 3. Avelumab Treatment Related Adverse Events (Incidence $\geq 5\%$) in the Ovarian Cancer Cohort

Events (n=75)	Treatment-Related AEs, all grades*, n (%)
Any event	52 (69.3)
Fatigue	12 (16.0)
Chills	9 (12.0)
Nausea	8 (10.7)
Diarrhea	8 (10.7)
Infusion-related reaction	6 (8.0)
Rash	6 (8.0)
Vomiting	4 (5.3)

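### The overall odds ratio for objective response is reported only if a Breslow-Day test is not rejected; otherwise the stratified CMH test has no matching overall estimate

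*SAP*

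**What the plan says.** SAP 6.2.2.3 sets out three steps for comparing objective response between arms.

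- A CMH test stratified by the randomization factors, at one-sided 0.025. It is run without conditions.
- An odds ratio, announced without conditions: "The stratified odds ratio in terms of OR will also be estimated along with its 95% CI to compare study treatments".
- A Breslow-Day test that then decides which odds ratio is given. One branch opens "In case the null hypothesis of homogeneity of odds ratios across strata is not rejected at the 2-sided alpha level of 0.05, the common odds"; there the Mantel-Haenszel estimate is used. In the other branch, "if the null hypothesis of homogeneity of odds ratio across all strata is rejected, the odds ratio per stratum will be calculated", each having an exact interval. No pooled measure is named for that branch.

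SAP 6.2.2 applies the tumor-related analyses to both BICR and investigator assessments, so the rule operates for two comparisons and two assessors. Other response output does not depend on it: the response rate per arm with a Clopper-Pearson interval (SAP 6.2.2.3; also Protocol 9.3.2), and odds ratios by subgroup in a forest plot (SAP 6.4, per BICR).

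**The concern.** The announcement of a stratified odds ratio and the rule that follows it do not agree. If Breslow-Day is rejected, the stratified odds ratio becomes a set of per-stratum values, while the CMH p-value still summarizes the comparison over all strata. The reader would have an overall test with no overall between-arm estimate beside it. Neither the arm-level rates nor the subgroup odds ratios fill that place: the first are not a contrast, and the second are not overall.

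The rule also differs from the SAP's treatment of a failed assumption elsewhere. In SAP 6.2.2.1, evidence against proportional hazards adds a restricted mean survival time analysis and leaves the hazard ratio in place; SAP 6.2.2.2 carries this over to PFS. For response, the assumption test withdraws the overall estimate.

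What is at stake is the presentation of a secondary endpoint: a table with a common odds ratio for some analyses and eight stratum values for another.

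**Working it through.** **Inputs from the documents**
- Strata: "Patients will be stratified by platinum-refractory or platinum-resistant status, number of prior regimens (1 vs 2 or 3), and bulky disease" (SAP 2.2). Three binary factors give 2 × 2 × 2 = 8.
- Size: "approximately 550 patients will be randomized in a 1:1:1 ratio to receive avelumab alone" (SAP 2.2). 550/3 is about 183 per arm.
- PLD: "response rates of 10-20%, median PFS times of 2.1-3.7 months" (Protocol 1.2.1).
- Avelumab: 8/75 = 10.7%, unconfirmed (Protocol 1.2.2.4). The Clopper-Pearson interval reproduces the stated 4.7% to 19.9%.

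The documents give no power or precision figure for the response odds ratio, so there is none to reproduce.

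**Stratum size.** 183/8 is about 23 per arm on average. At 10 to 20% response that is 2.3 to 4.6 responders per arm per stratum.

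**Precision**
- One average stratum, 2 vs 5 responders of 23: odds ratio about 2.9, exact 95% CI 0.41 to 33.
- One average stratum, 0 vs 3 responders of 23: infinite, with lower limit 0.42.
- Whole comparison at 10% vs 20%, unstratified approximation: odds ratio (0.2/0.8)/(0.1/0.9) = 2.25. SE of the log = √(1/18.3 + 1/164.7 + 1/36.6 + 1/146.4) = 0.308. 95% CI 2.25 × exp(±1.96 × 0.308) = 1.23 to 4.11.

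**Strata with an odds ratio of 0 or infinity.** Stratum shares are not in the documents, so they are assumed. Simulation used 2,000 trials per setting, 183 per arm, a common odds ratio and response rates of 10 to 20%.

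| Assumed refractory / one prior regimen / bulky | Mean number of 8 strata with odds ratio 0 or infinite |
|---|---|
| Equal eighths | 0.15 to 1.3 |
| 35 / 50 / 40% | 0.4 to 1.6 |
| 20 / 50 / 40% | 1.0 to 2.0 |
| 10 / 50 / 30% | 1.6 to 1.9 |

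A further 0 to 1.75 strata have no responder in either arm, so the odds ratio is undefined. Hand check of the lowest figure: with equal strata and 20% response, the chance of no responder in one stratum of one arm is (1 − 0.2/8)^183 = 0.0097, and 8 × 2 × 0.0097 × (1 − 0.0097) = 0.15.

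The per-stratum branch is used only after rejection. Given rejection, the mean is 0.6 to 3.0 strata. The chance of at least two runs from 0.06 (equal strata, 20% response) to 0.95 (about 10% response).

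**How often the branch is triggered**
- With a truly common odds ratio and 10 to 20% response, Breslow-Day rejects in about 3.5 to 5.5% of analyses. With both arms at 4% it rejects in 1.7 to 2.8%.
- Over four analyses, if independent: 1 − (1 − 0.035)^4 = 0.13 and 1 − (1 − 0.05)^4 = 0.19. At 5.5% the formula gives 0.20, but the simulation standard error near 5% is √(0.05 × 0.95/2000) = 0.5 percentage points, so 5.5% is not distinguishable from the nominal level.
- The four analyses are not independent: the comparisons share Arm C, and both assessors rate the same patients. With a shared control and an assumed 75 to 90% overlap of responders between assessors, the chance of at least one rejection was 10 to 16%.

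**Does the test find real heterogeneity?** With odds ratios of 1 vs 4, or 0.5 vs 3, in refractory vs resistant patients, its power was 27 to 57%. The Mantel-Haenszel estimate could be computed in every one of these runs.

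**The case against.** The rule is fully pre-specified with a fixed threshold, and declining to pool after homogeneity is rejected is a conventional choice. The stratum odds ratios come with exact intervals. Arm-level rates are always given, so a crude difference or odds ratio can be worked out. Protocol 9.3.2 plans nothing more than rates per arm. Response is outside the alpha-controlled hypotheses of SAP 5.1.1, and the chance trigger is about 1 in 20 or less per analysis.

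All of that stands, and it sets the severity. It does not answer the mismatch: the CMH p-value is kept after rejection while its estimate is dropped, and a crude odds ratio is not the stratified one. Nor does the test reliably mark the cases where pooling would mislead, given its power of 27 to 57%.

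A reader might infer more than the documents support:
- That eight stratum odds ratios would be the only effect measure. Arm rates with exact intervals and subgroup odds ratios remain.
- That several strata are bound to give 0 or infinity. This is likely near 10% response with uneven strata, but not with equal strata at 20%.
- That sparse strata inflate the trigger. The simulated rejection rate is at or below nominal, within simulation error.
- That the four results become non-comparable. The arm rates stay comparable throughout, and no comparison of odds ratios across the four analyses is planned.
- That response is the leading secondary endpoint. Protocol 2.2 and SAP 3.2.2 list it without rank.

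**Conclusion.** The point holds on the SAP's wording alone: an overall stratified odds ratio is announced and then made conditional, and the branch after rejection leaves the CMH test without a matching overall between-arm estimate. No simulation is needed for that conclusion.

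The size is small. The 3.5 to 5.5% per analysis assumes a common odds ratio and 10 to 20% response. The 13 to 19% over four analyses is an upper range that assumes independence. The number of degenerate strata rests on assumed stratum shares and cannot be fixed from the documents. No confirmatory conclusion depends on this odds ratio, so this is a free improvement of low severity.

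**What to change.** In SAP 6.2.2.3, remove the condition. Report the Mantel-Haenszel common odds ratio with its 95% CI for each comparison and each assessor. Give the Breslow-Day p-value as description. If it suggests heterogeneity, add stratum-level response counts and odds ratios with exact intervals as a supplement, and say how strata with no responders are shown.

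The cost is a sentence or two in the SAP and one conditional branch fewer in the program. No new data are needed and no other analysis changes. Protocol Section 9 records that the final analysis is complete; if the rejection branch was taken in any of the four analyses, the common odds ratio can be added from the existing data.
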